## 6. Human Research Protection

#### 6.1 Data confidentiality

Paper-based records will be kept in a secure location and only be accessible to personnel involved in the study. Computer-based files will only be made available to personnel involved in the study through the use of access privileges and passwords. Wherever feasible, identifiers will be removed from study-related information. Precautions are in place to ensure the data are secure by using passwords and encryption, because the research involves web-based surveys.

#### 6.2 Subject confidentiality

Research material will be obtained from participant surveys and wearable devices. All participants will provide informed consent for access to these materials. The data to be collected include data on participant characteristics and behaviors, daily adherence to an IF dietary pattern, and weekly weight and blood pressure measurements. Research material that is obtained will be used for research purposes only. The same procedure used for the analysis of automated data sources to ensure protection of patient information will be used for the survey data, in that patient identifiers will be used only for linkage purposes or to contact patients. The study identification number, and not other identifying information, will be used on all data collection instruments. All study staff will be reminded to appreciate the confidential nature of the data collected and contained in these databases. The Penn Medicine Academic Computing Services (PMACS) will be the hub for the hardware and database infrastructure that will support the project and is where the Way to Health web portal is based. The PMACS is a joint effort of the University of Pennsylvania's Abramson Cancer Center, the Cardiovascular Institute, the Department of Pathology, and the Leonard Davis Institute. The PMACS provides a secure computing environment for a large volume of highly sensitive data, including clinical, genetic, socioeconomic, and financial information. Among the IT projects currently managed by PMACS are: (1) the capture and organization of complex, longitudinal clinical data via web and clinical

applications portals from cancer patients enrolled in clinical trials; (2) the integration of genetic array databases and clinical data obtained from patients with cardiovascular disease; (3) computational biology and cytometry database management and analyses; (4) economic and health policy research using Medicare claims from over 40 million Medicare beneficiaries. PMACS requires all users of data or applications on PMACS servers to complete a PMACShosted cybersecurity awareness course annually, which stresses federal data security policies under data use agreements with the university. The curriculum includes Health Insurance Portability and Accountability Act (HIPAA) training and covers secure data transfer, passwords, computer security habits and knowledge of what constitutes misuse or inappropriate use of the server. We will implement multiple, redundant protective measures to guarantee the privacy and security of the participant data. All investigators and research staff with direct access to the identifiable data will be required to undergo annual responsible conduct of research, cybersecurity, and HIPAA certification in accordance with University of Pennsylvania 334 regulations. Data will be stored, managed, and analyzed on a secure, encrypted server behind the University of Pennsylvania Health System (UPHS) firewall. This server was created for projects conducted by the Penn Medicine Nudge Unit related to physician and patient behavior at UPHS. All study personnel that will use this data are listed on the IRB application and have completed training in HIPAA standards and the CITI human subjects research. Data access will be password protected. Whenever possible, data will be deidentified for analysis.

### 6.3 Subject privacy

Interested participants will be directed to the Way to Health portal where they will be asked to enter data related to eligibility and their demographic characteristics. Enrollment will include a description of the voluntary nature of participation, the study procedures, risks and potential benefits in detail. The enrollment procedure will provide the opportunity for potential participants to ask questions and review the consent form information prior to making a decision to participate. Participants will be told that they do not have to answer any questions if they do not wish and can drop out of the study at any time, without affecting their medical care or the cost of their care. They will be told that they may or may not benefit directly from the study and that all information will be kept strictly confidential, except as required by law. Subjects will have access to a copy of the consent document. All efforts will be made by study staff to ensure subject privacy.

#### 6.4 Data disclosure

The following entities, besides the members of the research team, may receive protected health information (PHI) for this research study: Twilio, Inc., the company which processes some 359 study-related messages. Twilio will store patients' phone numbers on their secure computers. Qualtrics, Inc., the company which processes most study-related surveys. Qualtrics will house de-identified answers to these surveys on their secure servers. The Office of Human Research Protections at the University of Pennsylvania -Federal and state agencies (for example, the Department of Health and Human Services, the National Institutes of Health, and/or the Office 364 for Human Research Protections), or other domestic or foreign government bodies if required by 365 law and/or necessary for oversight purposes.

#### 6.5 Data safety and monitoring

The Principal Investigator will be responsible for monitoring the study. All participants will be given anticipatory guidance on when to seek medical attention. In addition, participants will be asked to report to the study team any injuries or medical care that they feel resulted from participation in the study. They can either call the study team or send an email. The research coordinator will call the participant to collect information regarding the issue and then the PI will review and determine whether it is ok to proceed, further investigation is needed, or the participant should stop the study. For this study there will be no stopping rules or endpoints and thus no planned interim analyses.

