# 3. Study Design

#### 3.1. General Overview

The IFAST study is a two-arm randomized controlled trial aimed at evaluating whether a soft commitment device increases uptake and adherence to an intermittent fasting dietary pattern compared with control in patients with hypertension and obesity. The study will randomize 34 patients with hypertension and obesity to a 12-week intervention employing a commitment pledge, involvement of a supportive partner, setting of implementation intentions, and multiple daily reminder text messages or to an attention control involving daily text messages alone.

Following the intervention, there will be a 6-week follow-up period (see study protocol figure below).

The study will be conducted using Way to Health, a research information technology platform at the University of Pennsylvania used previously for behavioral interventions.

After institutional review board (IRB) approval of the study, patients who meet the eligibility criteria will be approached in select cardiology clinics and invited to participate. Those who qualify and express interest will provide informed consent to the study procedures via the Way to Health platform. All patients will receive a blood pressure cuff and scale, which will be used to measure blood pressure and weight weekly. Within the Way to Health platform, patients will be randomized to the intervention or control arms. All other management decisions are completely at the discretion of the care providers. Data capture will include:

- **Baseline case report form** (for each patient) collecting clinical information abstracted from the medical record
- **Baseline survey** collected via the Way to Health platform including psychometric questions, dietary patterns, and experiences with weight loss and dieting
- Daily adherence to an intermittent fasting dietary pattern collected via self-report from text messages
- Weekly weight and blood pressure measurement collected via self-report from text messages

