#### 6.6 Risk/benefit

## 6.6.1 Potential study risks

Both arms will be instructed to pursue an IF dietary pattern, which has been shown to be generally safe across multiple studies. Potential adverse effects of IF include irritability, hunger, difficulty with concentration, development of an eating disorder, disrupted sleep, dehydration and dizziness, and feelings of guilt and increased stress. There is a theoretical risk of hypoglycemia and pancreatitis. At the start of the study, patients will be given information on risks of IF and guidance on when to seek medical attention. They will also be encouraged to consume plenty of fluids during their daily fasting period. Patients on insulin or insulin secretagogues will be excluded from participation, limiting the risk of iatrogenic hypoglycemia, but patients with diabetes mellitus will be asked about episodes of hypoglycemia via weekly text messages, and all patients will be asked about hospitalizations and emergency room visits via weekly text messages.

Another potential risk of this study is a breach of participant confidentiality. We will minimize this risk by using secure data methods as described previously. Names and addresses will be stored in encrypted databases. These data will be viewable only by the respective participants, the study coordinator(s) and the project manager(s). All other members of the research team will be able to view only participant ID numbers. Even the study arms will be identified by code letters until both the statistician and PI agree that analysis is complete.

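### After a suspected harm the PI's only stopping action is to end the participant's study; a default of stopping fasting but keeping weekly follow-up would be a cheap, minor improvement

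*Combined protocol and SAP*

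**What the plan says.** Section 6.5 asks participants to report "any injuries or medical care that they feel resulted from participation in the study", by telephone or email. The coordinator rings back for details. The decision after that call is worded as follows: "the PI will review and determine whether it is ok to proceed, further investigation is needed, or the participant should stop the study". The last of these three outcomes is the only one that stops anything. The document does not say whether it means the diet, the study contact, or both.

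Section 6.6.1 describes the exposure and the scheduled safety monitoring. "Both arms will be instructed to pursue an IF dietary pattern", so a PI-directed stop can arise in either arm. For monitoring, participants with diabetes get a weekly text question on hypoglycemia. A second weekly question goes to everyone: "all patients will be asked about hospitalizations and emergency room visits via weekly text messages". The same section lists development of an eating disorder among the possible adverse effects of fasting.

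Section 3.1 lists "Weekly weight and blood pressure measurement collected via self-report from text messages" as a data source, and every participant is given a cuff and a scale. Both descriptions of the arms in Section 4.4 include the weekly weight and blood pressure text. Change in systolic pressure and in weight at 12 and 18 weeks are secondary outcomes (Section 5.1).

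Section 5.3 keeps in the analysis everyone who received at least one fasting text, including people who did not complete the protocol. It counts unreported days as non-adherent. It names mixed effects models for blood pressure and weight, with no separate missing-data rule. Sections 4.1 and 6.3 cover voluntary withdrawal only.

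**The concern.** The possible cause of harm is the fasting. The weekly texts only observe it, so the two can be separated. The PI's stopping action does not separate them.

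Two things follow if the action is applied as written.

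- **Safety.** The scheduled questions on hospitalizations, emergency room visits and hypoglycemia would end just after an event that the PI judged serious enough to stop for. The coordinator's call covers the event itself. Nothing scheduled covers the weeks after it.
- **Secondary outcomes.** Later blood pressure and weight readings would be missing for reasons that may relate to how the person responded to fasting. A mixed model would use the readings before the stop and infer the rest from people who continued. Keeping such people in the analysis set, as Section 5.3 does, does not secure their later readings.

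**Working it through.** **1. The plan's nearest figure.** Section 5.2 gives about 50% power for a 10 mmHg difference in blood pressure with SD 15 and 17 per arm. No alpha is stated; two-sided 5% is assumed here.

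- Standard error of the difference: 15 × √(2/17) = 5.14 mmHg.
- Power, normal approximation: Φ(10/5.14 − 1.96) = 0.493.

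The stated figure is reproduced, and 5.14 mmHg is the yardstick below.

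**2. Weekly readings lost per stopped participant.** The follow-up length differs between sections: 18 weeks (3.1, 5.1 and the commitment arm), 16 weeks for controls (4.4.1, Attention control), and a 16-week study period (4.5). All three totals are shown.

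| Schedule | Total readings | Lost if stopped just after week 4 | Lost if stopped just after week 12 |
|---|---|---|---|
| Both arms 18 weeks | 34 × 18 = 612 | 14 (2.3%) | 6 (1.0%) |
| Commitment 18, control 16 | 17 × 18 + 17 × 16 = 578 | 12 or 14 (2.1% or 2.4%) | 4 or 6 (0.7% or 1.0%) |
| Both arms 16 weeks | 34 × 16 = 544 | 12 (2.2%) | 4 (0.7%) |

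The same number of weekly safety questions is lost if they run over the same weeks, which is an assumption.

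**3. Possible shift in systolic pressure.** The documents give neither a stop rate nor a difference between people who stop and people who continue, so both are assumed: k = 1 or 2 of 17 stopped in one arm, with mean change differing by d = 5 or 10 mmHg. If those who continue have mean m, the full-arm mean is [(17 − k)m + k(m + d)]/17 = m + kd/17. Leaving out the stopped participants therefore shifts the arm mean by kd/17.

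| k | d (mmHg) | Shift (mmHg) | Shift / 5.14 |
|---|---|---|---|
| 1 | 5 | 0.29 | 0.06 |
| 1 | 10 | 0.59 | 0.11 |
| 2 | 5 | 0.59 | 0.11 |
| 2 | 10 | 1.18 | 0.23 |

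For these inputs the shifts are upper bounds. They treat a stopped participant as contributing nothing, whereas the mixed model keeps the earlier readings. They also put every stop in one arm, whereas both arms fast and similar stops in each would partly cancel.

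**4. Power.** If stopped participants contributed nothing, power for systolic pressure would fall from 0.493 at 17 per arm to 0.470 at 16, 0.447 at 15 and 0.422 at 14. For weight (3 kg, SD 5 kg) it would fall from 0.417 to 0.396, 0.376 and 0.355. That is about 2 points per participant lost from each arm, and again an upper bound.

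**5. Primary outcome.** A participant told to stop fasting is non-adherent from then on. If the daily text also stops, Section 5.3 scores the unreported days as non-adherent. The two routes give essentially the same value.

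**The case against.** The strongest objection is that the loss depends on the strictest reading of an undefined phrase. Section 6.5 does not say that data collection ends. The PI's other two outcomes are compatible with continued texts. A participant may stop fasting by choice, or on a clinician's advice, since "All other management decisions are completely at the discretion of the care providers", and keep replying. The consent pages are not in this file and may say more. All of this stands, and it narrows the gap to a stop directed by the PI after a reported event. It does not close it: no visible text provides for that case, and one sentence would settle either reading.

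A second objection concerns the remedy. If the full stop were simply replaced, the PI could no longer take someone off the study. A participant who develops an eating disorder may be harmed by weekly weighing prompts. This objection is right, and the full stop must remain.

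Three stronger readings are tempting, and the documents support none of them.

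- A reader might infer that harmed participants are abandoned. They are not: the coordinator calls, the PI reviews, and participants are told when to seek medical attention.
- A reader might infer that Section 5.3 contradicts Section 6.5. It does not: one defines who is analyzed, the other what the PI may do.
- A reader might infer bias in the primary outcome. Step 5 of the working shows why that does not follow.

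**Conclusion.** The point holds as a minor design improvement, not as an error in the plan. The PI has one undefined stopping action, and followed as written it ends the scheduled safety questions and the secondary-outcome readings together.

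The size is probably small and cannot be estimated from the documents. One stopped participant costs 0.7% to 2.4% of the trial's weekly readings for a stop just after week 12 or week 4. The 0.3 to 1.2 mmHg shift, 0.06 to 0.23 of a standard error, rests wholly on the assumed number of stops and the assumed difference, and is an upper bound for those inputs. It should not be read as a forecast of bias.

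The conclusion assumes that the stopping action ends the texts and that the removed consent pages do not say otherwise. The case for acting is the safety follow-up together with the negligible cost, not the numerical effect.

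**What to change.** In Section 6.5, keep the first two outcomes and put this in place of the third:

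*…or the participant should stop fasting (fasting instructions, reminders and partner updates cease, while weekly blood pressure, weight and safety texts continue to the end of scheduled follow-up unless the participant declines), or, if the PI judges that continued contact or self-weighing could be harmful, stop the study entirely.*

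The first of the two added options is the default. The daily fasting question may stop too, since unreported days already count as non-adherent. The voluntary-withdrawal text in Sections 4.1 and 6.3 needs no change.

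The cost is one sentence and a per-message switch on the platform; the cuffs, scales and weekly texts are already in place. The downsides are a few more texts to people who have stopped fasting, some of whom will not reply, so some readings will still be missing, and a PI judgement on when the weighing prompts should also end.

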#### 6.6 Risk/benefit

## 6.6.1 Potential study risks

Both arms will be instructed to pursue an IF dietary pattern, which has been shown to be generally safe across multiple studies. Potential adverse effects of IF include irritability, hunger, difficulty with concentration, development of an eating disorder, disrupted sleep, dehydration and dizziness, and feelings of guilt and increased stress. There is a theoretical risk of hypoglycemia and pancreatitis. At the start of the study, patients will be given information on risks of IF and guidance on when to seek medical attention. They will also be encouraged to consume plenty of fluids during their daily fasting period. Patients on insulin or insulin secretagogues will be excluded from participation, limiting the risk of iatrogenic hypoglycemia, but patients with diabetes mellitus will be asked about episodes of hypoglycemia via weekly text messages, and all patients will be asked about hospitalizations and emergency room visits via weekly text messages.

Another potential risk of this study is a breach of participant confidentiality. We will minimize this risk by using secure data methods as described previously. Names and addresses will be stored in encrypted databases. These data will be viewable only by the respective participants, the study coordinator(s) and the project manager(s). All other members of the research team will be able to view only participant ID numbers. Even the study arms will be identified by code letters until both the statistician and PI agree that analysis is complete.

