# 1.2. Effect of Intermittent Fasting on Metabolic Parameters

In contrast to the DASH diet, intermittent fasting (IF) is a dietary pattern that emphasizes temporal restriction of caloric intake rather than restricting the number of calories and/or changing the types of foods eaten. The simplest and most popular variation of IF involves restricting caloric intake to an 8-hour period each day, and consuming no calories for the other 16 hours (so-called 16:8 time-restricted feeding). In animal studies, IF has been shown to activate cellular pathways with potential disease-modifying benefits in a number of conditions. In small human studies, IF is associated with a reduction in SBP by 5-10 mmHg, LDL cholesterol by ~8 mg/dl, and weight by ~ 3 kg, though none of the studies of a time-restricted feeding regimen included concurrent controls. Some patients report that IF is easier to initiate and maintain than other dietary patterns, though this has not been tested empirically.

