#### 3.3.2. Exclusion Criteria

Patients are excluded if they meet any of the following criteria:

- 1. Unable or unwilling to provide informed consent, including but not limited to cognitive or language barriers (reading or comprehension)
- 2. Type 1 diabetes
- 3. Use of insulin or insulin secretagogues (sulfonylureas, metaglinides)
- 4. Use of medications that require food intake
- 5. Ongoing use of pharmacologic therapy for weight loss
- 6. Self-reported eating disorder
- 7. Other medical condition that could be harmed by intermittent fasting as judged by study physician
- 8. Anticipated life expectancy less than 6 months
- 9. Any other reason why it is not feasible to complete the entire 6-month study

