#### 6.6.3 Risk/benefit assessment

Anticipated risks of this study should be minimal and the risk/benefit ratio is very favorable. To minimize the chance for serious and unexpected adverse events, study participants will be screened through exclusion criteria for any health conditions that may be exacerbated by participating in this study. We have previously outlined the procedures that will be used to prevent a breach of participant data.

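### Insulin, insulin secretagogues and medicines that require food are excluded at entry only; no described on-study contact asks whether one has been started (low priority, cheap to mend)

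*Combined protocol and SAP*

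**What the plan says.** Section 3.3.2 has two medication exclusions that matter here. Criterion 3 reads "Use of insulin or insulin secretagogues (sulfonylureas, metaglinides" (closing parenthesis omitted here), and criterion 4 reads "Use of medications that require food intake". Section 6.6.1 gives the safety reason for criterion 3: "Patients on insulin or insulin secretagogues will be excluded from participation, limiting the risk of iatrogenic hypoglycemia". Section 6.6.3 describes the safeguard as screening: "study participants will be screened through exclusion criteria for any health conditions that may be exacerbated by participating in this study".

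Only type 1 diabetes is excluded as a diagnosis, and 6.6.1 plainly expects some patients with diabetes. Section 3.1 describes abstraction from the medical record for the baseline form and for nothing later. It also says "All other management decisions are completely at the discretion of the care providers".

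Both arms are asked to fast for at least 16 hours every day (4.4.1, both subsections). Section 1.2 defines the pattern as "restricting caloric intake to an 8-hour period each day, and consuming no calories for the other 16 hours". During the study, 6.6.1 adds that "patients with diabetes mellitus will be asked about episodes of hypoglycemia via weekly text messages", and that everyone is asked weekly about hospital and emergency-room use. Section 6.5 sets up a coordinator call and a review by the principal investigator, who can stop a patient's participation.

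**The concern.** The protocol treats these medicines as unsuitable to combine with a daily 16-hour fast. That judgment applies as much to a medicine started in week 3 as to one in use at enrollment, but the described safeguard acts once, at entry. A care provider may start such a medicine at any time and is not asked to tell the study team. The patient would then meet an exclusion criterion while still being told to fast. In the commitment arm, the patient would also receive two fasting reminders a day until week 12, under a signed pledge and with weekly adherence reports to a support partner. Control patients receive reminders only to answer the daily question.

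What is at stake is patient safety in a few individuals: the plan would learn of the event rather than of the exposure. The validity of the trial is not in question.

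**Working it through.** The plan gives no figure on this point, so there is none to reproduce. The check is a list of contacts followed by a rough count.

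**1. Every on-study contact described**

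| Contact | Section | Who | Asks about a new medicine? |
|---|---|---|---|
| Daily fasting question | 4.4.1 | both arms | no |
| Weekly weight and blood pressure text | 4.4.1 | both arms | no |
| Fasting reminders and weekly adherence summary | 4.4.1 | commitment arm, 12 weeks | no |
| Weekly hypoglycemia text | 6.6.1 | patients with diabetes | no, asks about episodes |
| Weekly hospital and emergency-room text | 6.6.1 | all | no, asks about visits |
| Standing request to report injury or care attributed to the study | 6.5 | all | only if the patient makes that link |
| End-of-study questionnaire | 4.5 | both arms | none described; topic is the fasting experience |

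No contact asks about new medicines, and no rule ties suspension of fasting to one.

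**2. How many new starts.** The documents give only N = 34 (5.2). Every rate below is an assumption.

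- Criterion 3: 34 × (share with type 2 diabetes, 20–40%) × (share of these starting insulin or a secretagogue, 2–10%). Low: 34 × 0.20 × 0.02 = 0.14. High: 34 × 0.40 × 0.10 = 1.36.
- Criterion 4: 34 × (share starting such a medicine, 1–3%) × (share that cannot be fitted into the 8-hour window, 25–75%). Low: 34 × 0.01 × 0.25 = 0.085. High: 34 × 0.03 × 0.75 = 0.765.
- Together: 0.14 + 0.085 ≈ 0.2, to 1.36 + 0.765 ≈ 2.1, or roughly 0 to 2 patients.

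The window factor is needed because many with-food medicines can be taken during the 8 eating hours. One taken with food twice daily about 12 hours apart cannot, since 12 exceeds 8.

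**3. Effect of a stop on the primary outcome.** Suppose one of 17 patients in an arm, fasting d days a week, is told to stop at week t. Under the 5.3 rule the later days count as non-adherent, so the arm mean falls by d × (18 − t)/18/17. With d = 5 (assumed):

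- t = 0: 5/17 = 0.29 days per week
- t = 9: 5 × 9/18/17 = 0.15
- t = 14: 5 × 4/18/17 = 0.07

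The target difference in 5.2 is 1 day per week. The shift cancels in expectation if stops are equally common and similarly timed in the two arms.

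**The case against.** The strongest reply is that the sponsor did not rely on screening alone. The sentence that cites the exclusion goes on to the weekly hypoglycemia question and the weekly hospital and emergency-room question, and 6.5 adds anticipatory guidance, a reporting route and the power to stop a patient. Anyone with known diabetes who starts insulin or a secretagogue already gets the hypoglycemia text. What remains is mainly criterion 4, at under one patient, and 6.6.1 names no harm from that combination. This stands, and it sets the priority. It does not remove the gap, because these routes respond to an event or to the patient's own attribution. A medicine prescribed at a routine visit would probably trigger neither.

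Three stronger readings are tempting, and the documents do not support them:

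- *Hypoglycemia risk was overlooked.* It was not; weekly event-based surveillance is described.
- *A new start would go unnoticed for about nine weeks.* If starts are spread evenly over 18 weeks, the mean time remaining is 18/2 = 9 weeks. That is not a detection time, because the existing texts and the 6.5 route could bring a start to light sooner.
- *Patients are never told to report new medicines.* The risk information, consent pages and text scripts are not in the text reviewed and may say so. The point is limited to the procedures described.

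**Conclusion.** The gap is real in the plan as written: two medication exclusions, one with an explicit safety rationale, are checked at entry and not again, while prescribing is open and the fasting instruction has no suspension condition tied to a new medicine. It is small. The count of roughly 0 to 2 of 34 patients rests wholly on assumed rates and treats everyone at risk under criterion 3 as having known type 2 diabetes. No estimate of harm can be made from the documents. This is a low-priority, inexpensive safety improvement. It gives no reason to doubt the trial's design or its analysis.

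**What to change.** Add one yes/no item to the weekly text in both arms: 'Since your last weekly reply, did you start insulin, another diabetes medicine, or a medicine you were told to take with food?' Wording it from the last reply carries over a missed week.

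A 'yes' triggers the coordinator call and investigator review already in 6.5, checked against criteria 3 and 4. If the call confirms insulin, a secretagogue, or a food-requiring medicine that does not fit the 8-hour window, suspend the fasting instruction and any commitment-arm reminders until the principal investigator has reviewed the case with the treating clinician.

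Keep the patient in the modified intention-to-treat set, keep the 5.3 rule for non-adherent days, and report the number and timing of such stops by arm. A further t test on days up to the stop is not worth adding: if adherence wanes, the shorter, earlier window would flatter the stopped patients.

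Cost: 17 × 16 + 17 × 18 = 578 extra items if control follow-up is the 16 weeks in 4.4.1, or 34 × 18 = 612 if it is 18. If 5–20% of patients answer 'yes' once or twice each (assumed), there would be 34 × 0.05 × 1 = 1.7 to 34 × 0.20 × 2 = 13.6, so about 2 to 14 calls plus any review time. Most would not meet either criterion. The item is still self-report, and a patient who persistently fails to reply could be missed.
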